#### 5.2.2 Specify inclusion/exclusion criteria for cohort entry and define the index date

Inclusion and exclusion criteria were adapted from the trial as closely as possible. Definitions for all inclusion/exclusion are provided in **Appendix A** and are summarized in the flowcharts below.

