#### 6.3.2 Study follow-up

Both as-treated (AT) and intention-to-treat (ITT) analysis will be conducted with treatment defined as the index drug on the day of cohort entry. Because adherence in the real-world databases is expected to be much worse than in the trial, the AT analysis is the **primary** analysis, as it targets the relative hazard of outcomes on treatment.

For the AT analysis, the follow-up will start the day after the initiation of sacubitril/valsartan or ACEi and will continue until the earliest date of the following events:

- The first occurrence of the outcome of interest,
- The date of end of continue registration in the database,
- End of the study period,
- Nursing home admission
  - Nursing home admissions are considered a censoring event because the data sources utilized typically provide little to no data on a patient, particularly on drug utilization, after admission. We will utilize this as an exclusion reason for cohorts for the same reason.
- The date of drug discontinuation, defined as the date of the last continuous treatment episode of the index drug (sacubitril/valsartan or ACEi) + a 30-day grace period,
- The date of switching from an exposure to comparator and vice versa,
- The date of switching to or initiation of any angiotensin II receptor blockers (ARBs), including combination medications containing ARBs,
- The date of switching to or initiation of aliskiren, including combination therapies.

For the ITT analyses, the censoring based on the switching and treatment discontinuation will be replaced with a maximum allowed follow-up time of 365 days.

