The primary outcome is a composite of death from cardiovascular causes or hospitalization for heart failure		
Measured 14 days after drug initiation in diagnosis position specified below and inpatient care setting:
 
Hospital admission for CHF (Inpatient only, any position)
 
ICD-9 diagnosis: 428.x, 398.91, 402.01, 402.11, 402.91, 404.01, 404.11, 404.91, 404.03, 404.13, 404.93
 
ICD-10 diagnosis: I50.1, I50.2x, I50.4, I50.81, I09.81, I11.0 (hypertensive heart disease with HF), I13.0 (hypertensive heart and chronic kidney disease with HF and stage 1 through stage 4 CKD), I13.2 (hypertensive heart and CKD with HF and with stage 5 CKD or ESRD)
 
CV death
 
Inpatient mortality - heart failure --
 
Mortality- Dependent on data source.
 
 
CV mortality
 
Information on CV mortality through data linkage with the National Death Index (NDI) will be available for Medicare and Optum Clininformatics.
 
All-cause inpatient mortality
 
 
Identified using the discharge status codes- Optum-
 
 
• 20 = EXPIRED
 
• 21 = EXPIRED TO BE DEFINED AT STATE LEVEL
 
• 22 = EXPIRED TO BE DEFINED AT STATE LEVEL
 
• 23 = EXPIRED TO BE DEFINED AT STATE LEVEL
 
• 24 = EXPIRED TO BE DEFINED AT STATE LEVEL
 
		Intermediate mapping in claims
INCLUSION CRITERIA				Poor mapping or cannot be measured in claims
1	Age ≥ 18 years	Age 18 years or older at drug initiation		Can't be measured in claims but not important for the analysis
2	NYHA functional class II-IV	
Measured 45 days prior to and including the day of oral drug initiation in generic prescription claims requiring 28 days supply of Loop or Thiazide diuretics
 
Loop Diuretics: Bumetanide, Furosemide, Torsemide, Ethacrynic acid
 
-OR-
 
Thiazide and Thiazide-like Diuretics: Hydrochlorothiazide, Chlorothiazide, Chlorthalidone, Indapamide, Metolazone, Cyclothiazide, Hydroflumethiazide, Bendroflumethiazide, Benztiazide, Methyclothiazide, Polythiazide
		

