# Appendix A

12	
History of heart transplant or on a transplant list or with LV assistance device
	
Measured from all available data to and including the day of drug initiation in any diagnosis position and inpatient or outpatient care setting
 
Heart Transplantation            ICD-9 diagnosis: V42.1, V49.83, 996.83            ICD-10 diagnosis: Z94.1, Z76.82, T86.20, T86.21, T86.22            ICD-9 procedure: 33.6, 37.51            ICD-10 procedure: 02YA020, 02YA021, 02YA022            CPT-4 code: 33935, 33945
 
LVAD/Implantable Heart            ICD-9 diagnosis: V43.2x            ICD-10 diagnosis: Z95.811, Z95.812            ICD-9 procedure: 37.60, 37.66            ICD-10 procedure: O2HA0RS, O2HA3RS, O2HA4RS, 5A02116, 5A02216, O2HA0QZ, O2HA3QZ, O2HA4QZ            CPT-4 code: 33975, 33976, 33979, 33981 - 33983, 33977, 33978, 33980
	
13	
History of severe pulmonary disease
	
Measured from all available data to and including day of drug initiation in any diagnosis position and in inpatient or outpatient care setting
 
Worsening Asthma/Status Asthmaticus            ICD-9 diagnosis: 493.01, 493.02, 493.11, 493.12, 493.2x, 493.91, 493.22            ICD-10 diagnosis: J45.21, J45.22, J45.901, J45.902
 
COPD/Chronic Tuberculosis            ICD-9 diagnosis: 491.xx, 492.xx, 494.x, 496, 506.4, 748.61, 011.5x            ICD-10 diagnosis: J41.x, J43.x, J47.x, J44.x, J68.4, Q33.4, A15.0
 
Pulmonary Fibrosis or Interstitial Lung Disease (ILD)            ICD-9 diagnosis: 515, 516.3x, 516.8, 516.9            ICD-10 diagnosis: J84.10, J84.111, J84.112, J84.113, J84.114, J84.115, J84.116, J84.117, J84.09, J84.2, J84.89, J84.9
 
Cystic Fibrosis            ICD-9 diagnosis: 277.0x            ICD-10 diagnosis: E84.xx
 
Pulmonary Hypertension/Other Pulmonary Heart Disease            ICD-9 diagnosis: 416 xx            ICD-10 diagnosis: I27.xx
 
Sarcoidosis
	
Pulmonary fibrosis/Interstitial lung disease:            Jones N, Schneider G, Kachroo S, et al. A systematic review of validated methods for identifying pulmonary fibrosis and interstitial lung disease using administrative and claims data. Pharmacoepidemiol Drug Saf. 2012;21(1):256-60. Available at: http://www.ncbi.nlm.nih.gov/pubmed/22262614.

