# Appendix A

19c Evidence of hepatic disease as determined by any one of the following: aspartate aminotransferase or alanine aminotransferase values exceeding 2x upper limit of normal at Visit 1, history of hepatic encephalopathy, history of oesophageal varices, or history of porto-caval shunt	
Measured from the start of all available data of drug initiation in any diagnosis position in inpatient and outpatient care setting
 
Hepatic Encephalopathy/Coma ICD-9 diagnosis: 070.0, 070.2x, 070.4x, 070.6, 070.71, 572.2 ICD-10 diagnosis: B15.0, B16.0, B16.2, B17.11, B19.0, B19.11, B19.21, K72.90, K72.91
 
Esophageal Varices ICD-9 diagnosis: 456.0, 456.1, 456.2x, 572.3 ICD-10 diagnosis: I85.xx, K76.6
 
Porto-Caval Shunt ICD-9 procedure: 39.1, 42.91 ICD-10 procedure: Codes are in the sheet 'PCShunt' CPT-4 code: 37182, 37183, 37241
 
Cirrhosis/Chronic Hepatic Diseases ICD-9 diagnosis: 571.0, 571.2, 571.3, 571.4, 571.5, 571.6 ICD-10 diagnosis: K70.0, K70.30, K70.9, K73.0, K73.2, K73.8, K73.9, K75.4, K74.0, K74.60, K74.69, K74.3, K74.4, K74.5, K74.1
 
NASH ICD-9 diagnosis: 571.8, ICD-10 diagnosis: K76.0
	
19d Current treatment with cholestyramine or colestipol resins	OR the following:	
20 Presence of any other disease with a life expectancy of 5 years	Measured 30 days prior to and including the day of index drug initiation for oral generic prescription claims of  Cholestyramine, Colestipol, Colesevelam	
21 Any Ivabradine use -- Approved in April 2015 (same year as Entresto)	Charlson Comorbidity Index > 10  Measure since 2015/all available data in drug prescription claims for any dispensings of  Generic name: Ivabradine Brand name: Corlanor	

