CV Medication - Loop diuretic; n (%)	1,078 (84.3%)	1,081 (84.5%)	-0.0055	645 (86.2%)	637 (85.2%)	0.0286	880 (87.5%)	859 (85.4%)	0.0614	1,958 (64.6%)	1,940 (64.0%)	0.0125	
CV Medication - Thiazide diuretics; n (%)	347 (11.5%)	155 (12.1%)	-0.0186	82 (11.8%)	88 (11.6%)	-0.0252	97 (9.6%)	119 (11.8%)	-0.0712	244 (8.0%)	274 (9.0%)	-0.0359	
CV Medication - Mineralocorticoid receptor antagonist; n (%)	573 (44.8%)	578 (45.2%)	-0.0080	393 (52.5%)	386 (51.6%)	0.0180	443 (44.0%)	427 (42.4%)	0.0323	1,016 (33.5%)	1,005 (33.1%)	0.0085	
CV Medication - Nitrate; n (%)	289 (22.6%)	277 (21.7%)	0.0217	172 (23.0%)	160 (21.4%)	0.0385	245 (24.4%)	230 (22.9%)	0.0353	534 (17.6%)	507 (16.7%)	0.0239	
CV Medication - PCSK9 Inhibitors; n (%)*	0 (0.0%)	3 (0.2%)	-0.0633	3 (0.2%)	1 (0.1%)	0.0448	3 (0.3%)	0 (0.0%)	0.0776	003 (0.1%)	003 (0.1%)	0.0000	
CV Medication - Use of Statins; n (%)	907 (70.9%)	926 (72.4%)	-0.0333	495 (66.2%)	475 (63.5%)	0.0566	728 (72.4%)	743 (73.9%)	-0.0339	1,635 (53.9%)	1,669 (55.0%)	-0.0221	
CV Medication - Use of other lipid-lowering drugs; n (%)	67 (5.2%)	68 (5.3%)	-0.0045	44 (4.9%)	48 (6.4%)	-0.0208	81 (8.1%)	71 (7.1%)	0.0377	148 (4.9%)	139 (4.6%)	0.0141	
CV Medication - CCB (non-dihydropyridine) - Non-combo with ACEI; n (%)	50 (3.9%)	58 (4.5%)	-0.0299	27 (2.9%)	27 (3.6%)	-0.0395	58 (5.8%)	59 (5.9%)	-0.0043	108 (3.6%)	117 (3.9%)	-0.0158	
CV Medication - CCB (dihydropyridine) - Non-combo with ACEI, ARB; n (%)	205 (16.0%)	208 (16.3%)	-0.0082	113 (15.1%)	110 (14.7%)	0.0112	133 (13.2%)	143 (14.2%)	-0.0291	338 (11.1%)	351 (11.6%)	-0.0158	
Other Comorbidity - Osteoporosis; n (%)	60 (4.7%)	57 (4.5%)	0.0095	21 (2.8%)	16 (2.1%)	0.0453	74 (7.4%)	74 (7.4%)	0.0000	134 (4.4%)	131 (4.3%)	0.0049	
Other Comorbidity - Dementia; n (%)	91 (7.1%)	93 (7.3%)	-0.0341	36 (4.8%)	36 (4.8%)	0.0000	94 (9.3%)	94 (9.3%)	0.0000	196 (6.5%)	185 (6.1%)	0.0165	
Other Comorbidity - Hypothyroidism; n (%)	40 (3.1%)	48 (3.8%)	-0.0384	28 (3.7%)	34 (4.5%)	-0.0404	76 (7.6%)	63 (6.3%)	0.0511	116 (3.8%)	111 (3.7%)	0.0053	
Other Comorbidity - Hyperthyroidism; n (%)	27 (2.1%)	22 (1.7%)	0.0293	9 (1.2%)	10 (1.3%)	-0.0090	25 (2.5%)	21 (2.1%)	0.0267	052 (1.7%)	043 (1.4%)	0.0243	
Other Comorbidity - Hyperkalemia; n (%)	78 (6.1%)	79 (6.2%)	-0.0042	45 (6.0%)	35 (4.7%)	0.0578	70 (7.0%)	68 (6.8%)	0.0079	148 (4.9%)	147 (4.8%)	0.0047	
Other Comorbidity - Depression; n (%)	207 (16.2%)	216 (16.9%)	-0.0188	76 (10.2%)	75 (10.0%)	0.0066	187 (18.6%)	182 (18.1%)	0.0129	394 (13.0%)	398 (13.1%)	-0.0030	

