Other Comorbidity - COPD; n (%)	378 (29.6%)	380 (29.7%)	-0.0022	108 (14.4%)	104 (13.9%)	0.0143	290 (28.8%)	297 (29.5%)	-0.0154	668 (22.0%)	677 (22.3%)	-0.0072	
Other Comorbidity - Pneumonia; n (%)	263 (20.6%)	270 (21.1%)	-0.0123	147 (19.7%)	139 (18.6%)	0.0280	185 (18.4%)	203 (20.2%)	-0.0456	448 (14.8%)	473 (15.6%)	-0.0223	
Other Comorbidity - Acute kidney injury (AKI); n (%)	284 (22.2%)	321 (25.1%)	-0.0683	158 (21.1%)	150 (20.1%)	0.0247	259 (25.7%)	253 (25.1%)	0.0138	543 (17.9%)	574 (18.9%)	-0.0	

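### At least a quarter of the matched patients behind Appendix B and the final power are ineligible under Exclusion #13 as printed, and no flowchart documents that cohort

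*Protocol*

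**What the plan says.** - **Where the rules stand.** Section 5.2.2: "Definitions for all inclusion/exclusion are provided in" Appendix A. It adds that the flowcharts summarize them.
- **Exclusion #13.** The trial criterion is "History of severe pulmonary disease". The claims version lists codes for several lung conditions, among them COPD (ICD-9 491, 492, 496; ICD-10 J41, J43, J44) and pulmonary hypertension/other pulmonary heart disease (416; I27). The window reads: "Measured from all available data to and including day of drug initiation in any diagnosis position and in inpatient or outpatient care setting". Section 5.3 has a row for this step, removing 463, 205 and 1,029 patients in Optum, MarketScan and Medicare.
- **Inclusion #2.** NYHA class is replaced by a prescription rule over the 45 days up to and including the index date, "requiring 28 days supply of Loop or Thiazide diuretics". Section 5.3 goes from Inclusion #1 to #3.
- **Exclusion #20.** Implemented as "Charlson Comorbidity Index > 10"; it has no row in Section 5.3.
- **Nursing home.** Section 6.3.2 makes admission a censoring event and adds: "We will utilize this as an exclusion reason for cohorts for the same reason". It also has no row.
- **Appendix B.** The matched table reports, among others, the rows "Other Comorbidity - COPD; n" and "CV Medication - Loop diuretic; n". Its 3,033 pairs are the input to the Final Power Assessment.

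**The concern.** A diagnosis that excludes a patient at any time up to the index date should be absent, or nearly so, from a baseline table of the eligible cohort. Here two such diagnoses are common in both arms of the matched set. Either the exclusion was not applied to this cohort, or it was applied with a code list other than the printed one. In both cases the document misdescribes who is being compared. The flowchart does not settle the matter, because it describes a different and much smaller cohort.

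At stake are the definition of the study population in a study meant to follow the trial's eligibility closely, and the number of pairs on which the stated power rests.

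**Working it through.** **1. The plan's own power.** Events = 2 × pairs × risk. Power = Φ(|ln HR| × √events / 2 − 1.96), the Schoenfeld formula for 1:1 groups. With 3,033 pairs, risk 0.21525 and HR 0.8, events = 1,305.7 and power = 0.981. This matches the stated 0.980850168, so the arithmetic is right; the question is which patients form the pairs.

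**2. Exclusion #13 in the matched table** (counts are reference/exposed). The overlap of the two conditions is not reported, so the number with either lies between the larger count and the sum in each database.

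| | Optum (1,279 per arm) | MarketScan (748) | Medicare (1,006) | All (3,033) |
|---|---|---|---|---|
| COPD | 378/380 | 108/104 | 290/297 | 776/781 |
| Pulmonary hypertension | 250/257 | 132/126 | 209/223 | 591/606 |
| Either, minimum | 378/380 | 132/126 | 290/297 | 800/803 |
| Either, maximum | 628/637 | 240/230 | 499/520 | 1,367/1,387 |

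Minimum share: 800/3,033 = 26.4% and 803/3,033 = 26.5%. Maximum: 45.1% and 45.7%. The printed pooled COPD counts, 668 and 677, are Optum plus Medicare only (378 + 290; 380 + 297), so I summed all three databases.

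The diagnoses are already there before matching. Pulmonary hypertension is recorded in 2,893 + 1,274 + 3,611 = 7,778 of 46,268 reference patients (16.8%) and in 506 + 218 + 369 = 1,093 of 5,371 exposed patients (20.4%). In the flowchart cohort the #13 step removes only 463/7,872 = 5.9%, 205/4,121 = 5.0% and 1,029/9,799 = 10.5% of those remaining.

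**3. Two cohorts.** Flowchart: 6,946 + 3,694 + 8,031 = 18,671. Pre-match balance table: 46,268 + 5,371 = 51,639. The ACE inhibitor arm is 4,217 + 2,218 + 6,293 = 12,728 in Section 7 and 46,268 in Appendix B. The exposed arm moves the other way, from 2,729 + 1,476 + 1,738 = 5,943 to 5,371.

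**4. Inclusion #2.** If no patient used both classes, those with neither number n − loop − thiazide; any overlap raises the figure.

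- Reference: (1,279 − 1,078 − 147) + (748 − 645 − 82) + (1,006 − 880 − 97) = 54 + 21 + 29 = 104 (3.4%).
- Exposed: (1,279 − 1,081 − 155) + (748 − 637 − 88) + (1,006 − 859 − 119) = 43 + 23 + 28 = 94 (3.1%).

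The Optum reference thiazide count prints as 347. I read 147, because 147/1,279 is the printed 11.5% and the pooled 244 equals 147 + 97. For MarketScan I used the counts 82 and 88 (11.0% and 11.8% of 748), since the percentages printed beside them do not fit.

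**5. Power if #13 is enforced as printed.** Take out the worse arm's violators and hold risk and HR fixed.

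- Minimum: 3,033 − 803 = 2,230 pairs, 960.0 events, power 0.933.
- Maximum: 3,033 − 1,387 = 1,646 pairs, 708.6 events, power 0.844.
- By database, with the database's own risk: Optum 0.727 falls to 0.576–0.443, MarketScan 0.408 to 0.348–0.296, Medicare 0.703 to 0.553–0.410.

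**The case against.** **Code lists and windows.** The code lists behind the Appendix B rows are not printed, and the full ICD-10 lists sit in an external folder, so the COPD row may not use the #13 codes. That is true but does not carry the weight needed. The only other COPD list in the document, in the ejection-fraction algorithm, adds just J42 to what #13 covers, which is unlikely to account for 14% to 30% of patients. The pulmonary hypertension row bears the same condition name as #13 and alone marks 591 and 606 patients, about one in five. A shorter covariate window, such as the 180-day default, does not help: a diagnosis inside it also lies inside all available data.

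**Fidelity to the trial.** A reader might infer that keeping these patients weakens the comparison with the trial. The documents do not support that. The trial criterion concerns severe disease, while the printed list takes any COPD code, so a cohort that keeps milder disease could be nearer to the trial or further from it.

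**Missing flowchart rows.** A reader might also infer that Exclusion #20 and the nursing-home rule were broken. That is not shown. The flowchart belongs to the November feasibility cohort and says nothing about the steps applied in December. A nursing-home rule could sit inside the row for cohort entry criteria. Appendix A also has a colour key for criteria that map poorly to claims; the colours are not visible in the text, so a deliberate omission of #20 or Inclusion #2 cannot be ruled out. These points stand.

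**Diuretics.** Neighbouring calcium-channel-blocker rows are labelled as leaving out combinations with ACE inhibitors or ARBs. If the thiazide row does likewise, the 3% shortfall could shrink or vanish. This stands too, so the count does not prove that the rule went unapplied.

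**Power.** Nor do the figures show an underpowered pooled analysis: the range above is 0.84 to 0.93.

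**Conclusion.** The point holds for Exclusion #13. As printed, the rule and the matched table cannot both be right: between 26% and about 45% of each arm carries an excluding diagnosis. It also holds that no flowchart documents the cohort that supplies the 3,033 pairs. For Inclusion #2 the missing step is a fact, and the 104 and 94 patients are a floor only if Appendix B counts every qualifying product. Exclusion #20 and the nursing-home rule are undocumented, no more.

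The main consequence is for who is analysed; the effect on pooled power is secondary. The power range assumes unchanged risk and HR after removal, and re-matching that loses only the worse arm's violators. Without re-matching, and if the minimum violators of the two arms never share a pair, 3,033 − 1,603 = 1,430 pairs remain and power is 0.79. Re-matching from the larger pre-match pool could recover some pairs.

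**What to change.** The protocol already stops here for review of balance and final power, so the change belongs before the outcome run:

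1. Reconcile the printed #13 code list with what was applied, and state the one list in force. Which list that should be is for the investigators.
2. For Inclusion #2, Exclusion #20 and the nursing-home rule, state whether each is applied. If it is, add its flowchart row; if not, mark it as not applied.
3. Use the same rules in all three databases.
4. Reissue the flowchart, Appendix B and the final power from that single cohort, with the code lists for the COPD, pulmonary hypertension and diuretic rows.

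The cost is one cohort rerun with updated tables and, if #13 is enforced as printed, fewer pairs and a lower stated power.

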# Appendix A

		Measured 365 days prior to drug initiation in any diagnosis position and inpatient care setting	
4b	Hospitalization for heart failure within the last 12 months	
Hospital Admission for CHF
 
ICD-9 diagnosis: 428.x, 398.91, 402.01, 402.11, 402.91, 404.01, 404.11, 404.91, 404.03, 404.13, 404.93
 
ICD-10 diagnosis: I50.1, I50.2x, I50.4, I50.814, I09.81, I11.0, I13.0, I13.2
	
5	Treatment with a stable dose of an ACE inhibitor or an ARB equivalent to enalapril 10 mg/day for at least 4 weeks before the screening visit; and treatment with a stable dose of a beta-blocker for at least 4 weeks prior to the screening visit, unless contraindicated or not tolerated	
Measured 47 days to 2 days prior to drug initiation in prescription claims requiring 28 days supply of oral ACEi or ARB -
 
ACE inhibitors' generic names for prescription claims: Enalapril, Captopril, Clazapril, Fosinopril, Lisinopril, Moexipril, Perindopril, Quinapril, Trandolapril, Zofenopril, Benazepril
 
-OR-
 
ARBs generic names for prescription claims: Candesartan, Eprosartan, Irbesartan, Losartan, Olmesartan, Telmisartan, Valsartan, Azilsartan
	
5a	Treatment with a stable dose of an ACE inhibitor or an ARB equivalent to enalapril 10 mg/day for at least 4 weeks before the screening visit	AND the following:	
5b	Treatment with a stable dose of a beta-blocker for at least 4 weeks prior to the screening visit, unless contraindicated or not tolerated	
Measured 45 days prior to index drug initiation in prescription claims (generic names) of an oral beta-blocker for at least 4 weeks (28 days)
 
Beta-blocker generic names for prescription claims: Acebutolol, Atenolol, Betaxolol, Bisoprolol, Carvedilol, Esmolol, Labetalol, Metoprolol, Metiranolol, Nebivolol, Nadolol, Propranolol, Pindolol, Sotalol, Penbutolol, Oxprenolol
	
6	Although not required, the protocol specified that an aldosterone antagonist should also be considered in all patients, taking account of renal function, serum potassium, and tolerability. If given, the dose of aldosterone antagonist should be stable for at least 4 weeks prior to the screening visit		
EXCLUSION CRITERIA			
1	History of hypersensitivity or allergy to any of the study drugs, drugs of similar chemical classes, ACE inhibitors (ACEIs), ARBs, or neprilysin inhibitors, as well as known or suspected contraindications to the study drugs		
2	Previous history of intolerance to recommended target doses of ACEIs or ARBs		
3	Known history of angioedema	
Measured from the start of all available data to index drug initiation in any diagnosis position and inpatient or outpatient care setting
 
ICD-9 diagnosis: 995.1 ICD-10 diagnosis: T78.3x
	
4	Requirement for treatment with both ACEIs and ARBs	
Measured 180 days prior to and including day of drug initiation in prescription claims (generic names) for any of oral ACEi and ARB for two subsequent dispensings
 
ACE inhibitors' generic names for prescription claims: Enalapril, Captopril, Clazapril, Fosinopril, Lisinopril, Moexipril, Perindopril, Quinapril, Ramipril, Trandolapril, Zofenopril, Benazepril
 
-AND-
 
ARBs generic names for prescription claims: Candesartan, Eprosartan, Irbesartan, Losartan, Olmesartan, Telmisartan, Valsartan, Azilsartan
	
5	Current acute decompensated heart failure (exacerbation of chronic heart failure manifested by signs and symptoms that may require intravenous therapy)	
Measured 7 days prior to and including day of drug initiation in any diagnosis position and inpatient and emergency care setting
 
ICD-9 diagnosis: 428.41, 428.43 ICD-10 diagnosis: I50.23, I50.41, I50.43
	
6	Symptomatic hypotension and/or a systolic blood pressure <100 mmHg at Visit 1 (screening) or <95 mmHg at Visit 3 or at Visit 5 (randomization)	
Measured 30 days prior to and including day of drug initiation in any diagnosis position and inpatient or outpatient care setting
 
Hypotension: ICD-9 diagnosis: 458.xx, 785.5x ICD-10 diagnosis: I95.xx, R57.xx
	

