### 5.3 Flowchart of the study cohort assembly

	Optum		MarketScan		Medicare*	
	Less Excluded Patients	Remaining Patients	Less Excluded Patients	Remaining Patients	Less Excluded Patients	Remaining Patients
All patients		77,673,639		200,203,908		23,466,175
Did not meet cohort entry criteria	-73,445,846	4,227,793	-196,533,760	3,670,148	-18,348,713	5,117,462
Excluded due to insufficient enrollment	-623,954	3,603,839	-340,051	3,330,097	-1,288,867	3,828,595
Excluded due to prior use of referent	-3,168,921	434,918	-2,967,886	362,211	-3,495,789	332,806
Excluded due to prior use of exposure	-29,778	405,140	-12,511	349,700	-33,013	299,793
Excluded because patient qualified in >1 exposure category	-8	405,132	-3	349,697	-9	299,784
Excluded based on Age	0	405,132	-1	349,696	0	299,784
Excluded based on Gender	-39	405,093	0	349,696	0	299,784
Excluded based on Inclusion #1 - Age >=18 years old	-624	404,469	-1,354	348,342	-721	299,063
Inclusion #3 - HFpEF prediction algorithm applied to reference group†	-381,531	22,938	-337,242	11,100	-259,816	39,247
Excluded based on Inclusion #4b - Hospitalization for HF within the last 12 months	-9,321	13,617	-4,618	6,482	-10,685	28,562
Excluded based on Inclusion #5a - ACEis or ARBs	-1,224	12,393	-385	6,097	-1,534	27,028
Excluded based on Inclusion #5b - Beta-blockers	-673	11,720	-248	5,849	-2,128	24,900
Excluded based on Exclusion #3 - Known history of angioedema	-56	11,664	-29	5,820	-200	24,700
Excluded based on Exclusion #4 - Treatment with both ACEis AND ARBs	-15	11,649	-9	5,811	-34	24,666
Excluded based on Exclusion #5 - Acute decompensated HF	-1,060	10,589	-435	5,376	-5,457	19,209
Excluded based on Exclusion #6 - Symptomatic hypotension	-734	9,855	-240	5,136	-1,964	17,245
Excluded based on Exclusion #7 - Low eGFR / renal dysfunction	-1,064	8,791	-403	4,733	-2,833	14,412
Excluded based on Exclusion #8 - Hyperkalemia	-57	8,734	-14	4,719	-116	14,296
Excluded based on Exclusion #9 - ACS, Stroke, TIA, CABG, PCI, Other CV Procedures, Carotid Angioplasty	-765	7,969	-546	4,173	-2,912	11,384
Excluded based on Exclusion #11 - Implantation of CRT device	-41	7,928	-19	4,154	-1,550	9,834
Excluded based on Exclusion #12 - History of heart transplant or LVAD	-56	7,872	-33	4,121	-35	9,799
Excluded based on Exclusion #13 - History of severe pulmonary disease	-463	7,409	-205	3,916	-1,029	8,770
Excluded based on Exclusion #14 - Diagnosis of peripartum- or chemotherapy-induced cardiomyopathy	-38	7,371	-34	3,882	-60	8,710

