# Appendix A

11	ACE inhibitor	Prescription claims for: Benazepril, captopril, enalapril, fosinopril, lisinopril, moexipril, perindopril, quinapril, ramipril, trandolapril	0.221748	Measured 180 days prior to and including the date of index drug initiation	6 months prior to index date + index date + 30days post-index
12	Index diagnosis recorded during an outpatient visit	Any diagnosis position in an outpatient care setting ICD-9 diagnosis: 428.x, 398.91, 402.01, 402.11, 402.91, 404.01, 404.11, 404.91, 404.03, 404.13, 404.93 ICD-10 diagnosis: I50.1, I50.2x, I50.4x, I50.814, I09.81, I11.0, I13.0, I13.2	-0.187191	Measured between 180 days prior to and including the date of drug initiation and pick claim closest to the index initiation	on index date
13	Mineralocorticoid receptor antagonist	Prescription claims for: Eplerenone, spironolactone	0.166008	Measured 180 days prior to and including the date of index drug initiation	6 months prior to index date + index date + 30days post-index
14	Anemia	ICD-9 diagnosis: 280.xx - 285.xx ICD-10 diagnosis: Please copy from ICD-10 codes tabs for anemia	-0.165353	Measured 180 days prior to and including the date of index drug initiation	6 months prior to index date + index date + 30days post-index
15	Valve disorder	ICD-9 diagnosis: 394.x - 397.x, 398.9x, V42.2, V43.3 ICD-10 diagnosis: Please copy from ICD-10 codes tabs for valve disorder ICD-9 procedure: 35.1x, 35.2x ICD-10 procedure: Please copy from ICD-10 codes tabs for valve disorder CPT code: 33660-33665, 33400-33403, 33420-33430, 33460, 33463-33468, 33475, 33496, 0257T, 0258T, 0259T, 0262T	-0.163684	Measured 180 days prior to and including the date of index drug initiation	6 months prior to index date + index date + 30days post-index
16	Digoxin	Prescription claims for: Digoxin	0.163224	Measured 180 days prior to and including the date of index drug initiation	6 months prior to index date + index date + 30days post-index
17	Thiazide diuretic	Prescription claims for: Bendroflumethiazide, Benztiazide, Chlorothiazide, Chlorthalidone, Hydrochlorothiazide, Indapamide, Methyclothiazide, Metolazone, Polythiazide, Quinethazone, Trichlormethiazide	-0.160819	Measured 180 days prior to and including the date of index drug initiation	6 months prior to index date + index date + 30days post-index

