CV Comorbidity - Hypertension; n (%)	1,026 (80.2%)	1,020 (79.7%)	0.0125	446 (59.6%)	446 (59.6%)	0.0000	830 (82.5%)	835 (83.0%)	-0.0132	1,856 (61.2%)	1,855 (61.2%)	0.0000	
CV Comorbidity - Unstable Angina (Inpatient or Outpatient); n (%)	161 (12.6%)	173 (13.5%)	-0.0267	78 (10.4%)	81 (10.8%)	-0.0130	146 (14.5%)	139 (13.8%)	0.0201	307 (10.1%)	312 (10.3%)	-0.0066	
CV Comorbidity - Implantation of CRT device; n (%)	428 (33.5%)	409 (32.0%)	0.0320	239 (32.0%)	239 (32.0%)	0.0000	193 (19.2%)	205 (20.4%)	-0.0301	621 (20.5%)	614 (20.2%)	0.0075	
CV Comorbidity - Stable Angina; n (%)	232 (18.1%)	241 (18.8%)	-0.0180	94 (12.6%)	79 (10.6%)	0.0625	203 (20.2%)	184 (18.3%)	0.0482	435 (14.3%)	422 (14.0%)	0.0086	
CV Comorbidity - Stroke/TIA; n (%)	81 (6.3%)	101 (7.9%)	-0.0623	45 (4.9%)	48 (5.2%)	-0.0042	82 (8.3%)	90 (9.9%)	-0.0214	164 (5.4%)	191 (6.3%)	-0.0384	
CV Comorbidity - Peripheral Vascular Disease (PVD) or PVD Surgery; n (%)	192 (15.0%)	189 (14.8%)	0.0056	69 (9.2%)	68 (9.3%)	0.0026	220 (22.9%)	228 (22.7%)	0.0189	422 (12.9%)	427 (14.1%)	-0.0058	
CV Comorbidity - Myocardial Infarction; n (%)	450 (35.2%)	447 (34.9%)	0.0063	190 (25.4%)	182 (24.3%)	0.0255	363 (36.0%)	362 (36.0%)	0.0021	813 (26.7%)	809 (26.6%)	0.0023	
CV Comorbidity - Atrial fibrillation; n (%)	576 (45.0%)	562 (43.9%)	0.0221	258 (34.5%)	275 (36.8%)	-0.0480	537 (53.4%)	524 (52.1%)	0.0260	1,113 (36.7%)	1,086 (35.8%)	0.0187	
CV Comorbidity - CABG/PCI; n (%)	478 (37.4%)	478 (37.4%)	0.0000	142 (19.0%)	140 (17.9%)	0.0790	369 (36.7%)	374 (37.2%)	-0.0104	847 (27.9%)	852 (28.1%)	-0.0045	
CV Medication - ACE Inhibitors; n (%)	1,279 (100.0%)	1,279 (100.0%)	#DIV/0!	748 (100.0%)	748 (100.0%)	#DIV/0!	1,006 (100.0%)	1,006 (100.0%)	#DIV/0!	2,285 (75.3%)	2,285 (75.3%)	0.0000	
CV Medication - Use of ARBs; n (%)	118 (9.2%)	127 (9.3%)	-0.0238	89 (11.9%)	92 (12.3%)	-0.0123	75 (7.5%)	81 (8.1%)	-0.0224	193 (6.4%)	208 (6.9%)	-0.0201	
CV Medication - Beta blocker; n (%)	1,273 (99.5%)	1,273 (99.5%)	0.0000	747 (99.7%)	746 (99.7%)	0.0448	998 (99.2%)	999 (99.3%)	-0.0116	2,271 (74.9%)	2,272 (74.9%)	0.0000	
CV Medication - Digoxin; n (%)	162 (12.7%)	158 (12.4%)	0.0091	104 (13.9%)	106 (14.2%)	-0.0368	172 (17.1%)	160 (15.9%)	0.0323	394 (11.0%)	318 (10.5%)	0.0161	
CV Medication - SGLT-2 Inhibitors; n (%)	48 (3.8%)	42 (3.3%)	0.0270	18 (2.4%)	22 (2.9%)	-0.0311	2 (2.0%)	5 (5.0%)	-0.0508	050 (1.6%)	047 (1.5%)	0.0081	

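### The ACE-inhibitor list in Inclusion 5a omits ramipril, so patients treated only with ramipril fail a criterion they meet

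*Protocol*

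**What the plan says.** All references are to the protocol.

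- **Appendix A, Inclusion 5/5a.** The trial criterion is treatment for at least four weeks with a stable ACE inhibitor or ARB dose "equivalent to enalapril 10 mg/day". The claims version is "Measured 47 days to 2 days prior to drug initiation in prescription claims requiring 28 days supply of" an oral ACE inhibitor or ARB from two lists of generic names. The end of the ACE-inhibitor list reads "Perindopril, Quinapril, Trandolapril, Zofenopril, Benazepril", going straight from quinapril to trandolapril.
- **Appendix A, Exclusion 4** (treatment with both classes). The same stretch of its ACE-inhibitor list reads "Quinapril, Ramipril, Trandolapril, Zofenopril, Benazepril".
- **Appendix A, ejection-fraction algorithm, ACE inhibitor row.** The list contains "moexipril, perindopril, quinapril, ramipril, trandolapril".
- **Section 5.1.** The comparator is widened from enalapril to all ACE inhibitors, on the ground that the class is expected to act alike on the outcome.
- **Section 5.3.** The flowchart applies the rule as its own step, "Excluded based on Inclusion #5a - ACEis or ARBs", in all three databases.

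**The concern.** Three lists in one appendix are meant to identify the same drug class, and one of them differs by a single name. The one that differs decides entry to the cohort.

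Nothing in the protocol gives a reason for treating ramipril differently at this step. Ramipril counts as an ACE inhibitor when dual therapy is looked for (Exclusion 4) and when ejection-fraction class is predicted. It does not count when prior treatment is verified. A patient with 28 days of ramipril in the window, and no other listed ACE inhibitor or ARB there, meets the clinical criterion and fails the coded one.

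At stake are the correctness of the eligibility rule and the reproducibility of the cohort. Anyone who rebuilds the cohort from Appendix A will drop these patients.

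**Working it through.** **1. Compare the lists.**

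| List in Appendix A | Agents | Ramipril |
|---|---|---|
| Inclusion 5/5a | 11 | no |
| Exclusion 4 | 12 | yes |
| Ejection-fraction algorithm | 10 | yes |

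Exclusion 4 minus 5a leaves ramipril only, and 5a minus Exclusion 4 leaves nothing. The algorithm list minus 5a also leaves ramipril only.

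**2. Bound the number affected (Section 5.3).** The flowchart subtractions at 5a are internally correct.

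| Database | Before 5a | Removed | After 5a | Share removed |
|---|---|---|---|---|
| Optum | 13,617 | 1,224 | 12,393 | 9.0% |
| MarketScan | 6,482 | 385 | 6,097 | 5.9% |
| Medicare | 28,562 | 1,534 | 27,028 | 5.4% |
| Total | 48,661 | 3,143 | 45,518 | 6.5% |

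The 3,143 include everyone who fails 5a for any reason, in both arms. The protocol does not say how many were ramipril users, so this is a ceiling and not an estimate.

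Many would also fall to later exclusions. Of the 45,518 left after 5a, 6,946 + 3,694 + 8,031 = 18,671 reach the final cohort (41.0%). At that yield the ceiling becomes 3,143 × 0.410 ≈ 1,290 patients. With each database's own yield it is 686 + 233 + 456 = 1,375.

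**3. Reproduce the final pooled power.** Inputs from the final power assessment: 3,033 pairs, risk 215.25 per 1,000, HR 0.8, two-sided alpha 0.05.

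- Events: D = 2 × 3,033 × 0.21525 = 1,305.7, as stated.
- Power = Φ(√D / 2 × |ln 0.8| − 1.96) = Φ(18.067 × 0.22314 − 1.96) = Φ(2.072) = 0.981. The protocol gives 0.980850168.

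**4. Power if the gap is closed.** Assume matched pairs grow in proportion to the patients passing 5a.

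- *Extreme case, all 3,143 are ramipril users.* Pairs = 3,033 × 48,661 / 45,518 = 3,242; D = 2 × 3,242.4 × 0.21525 = 1,395.9; power 0.986. Scaling within each database gives 1,405 + 795 + 1,063 ≈ 3,264 pairs, D = 1,405.0 and power 0.987.
- *5% to 25% of them are ramipril users (assumed shares, pooled scaling).* Pairs 3,043 to 3,085; D = 1,310.2 to 1,328.2; power 0.981 to 0.982.

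The proportional scaling is a rough device. The pre-match reference group in Appendix B (46,268) is not the one in Section 7 (4,217 + 2,218 + 6,293 = 12,728), so the flowchart cannot be tied exactly to the matched sample. The conclusion that power hardly moves does not depend on that precision.

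**The case against.** **It may be a slip on the page only.** The header of Appendix A sends readers to an external folder for details and missing information. The text available here was machine-read from a PDF, and some drug names elsewhere are visibly garbled. The executed code may include ramipril. That is possible but cannot be shown, and the operative list as it stands is wrong. It does mean that nobody can say from the document that patients were in fact dropped.

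**The effect is tiny.** This stands. The ceiling is loose and power barely changes. In addition, Section 5.2 bars comparator patients with any ACE inhibitor fill in the prior 60 days. Read literally, a comparator patient with a ramipril fill in the 5a window is already out, so the gap falls mainly on sacubitril/valsartan initiators coming from ramipril. No bias in the hazard ratio has been demonstrated. The small size lowers the weight of the point but does not make the list correct.

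**A stronger reading concerns dose.** A reader might infer that 5a is also defective because it drops the trial's dose threshold. Exclusion 2 ("Previous history of intolerance to recommended target doses of ACEIs or ARBs") shows no coded definition, and the readable Appendix B rows, such as "CV Medication - ACE Inhibitors; n", carry prior use only as yes/no flags. From this the reader might conclude that pre-index dose confounds the primary comparison and must enter the propensity score. The document does not support that conclusion:

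- Section 5.2.2 says that the criteria are adapted from the trial as far as possible, Section 1 acknowledges database limitations, and Section 6.1 openly accepts both drugs at any dose.
- No dose distribution is given, so neither the size nor the direction of any bias can be stated.
- Under the 60-day washout, a comparator patient's last ACE inhibitor fill before index would be more than 60 days old, while the exposed arm has no such limit. A last-dose covariate would therefore mean different things in the two arms.

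The missing dose term is a limitation of the emulation and may be noted as one.

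**Conclusion.** The point holds as an error in an operative eligibility list. Inclusion 5a omits ramipril, two other ACE-inhibitor lists in the same appendix include it, and the comparator is the whole class. As written, the rule excludes some patients who meet the criterion it implements.

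The size is small and not exactly known: at most 3,143 of 48,661 patients (6.5%) at that step, with pooled power going from 0.981 to no more than about 0.986 to 0.987 under the most extreme assumption. The point rests on the printed list being the one applied, which the document alone cannot confirm. It is about correct eligibility and a reproducible cohort. It is not evidence of a biased hazard ratio or of an underpowered study, and it does not extend to dose.

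**What to change.** 1. Add ramipril to the ACE-inhibitor list under Inclusion 5/5a in Appendix A, so that it matches the list under Exclusion 4.
2. Check the executed cohort code and state whether ramipril was included. If it was, only the document needs correcting.
3. If it was not, re-run the Section 5.3 flowchart, the propensity-score match, the Appendix B balance table and the final power figures before any outcome analysis. The stop for review that the protocol places after the balance and final power steps is the natural point for this.

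The cost is one name in a code list and, at worst, one re-run of existing programs. Matched numbers should change little.

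The authors may also add a sentence stating that 5a does not implement the trial's dose threshold. A dose covariate in the propensity score or a dose-restricted sensitivity analysis would be optional and is not required by this point.
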